OCA is another synthetic secondary bile acid which has only recently been approved by the FDA and EMA for treatment of PBC [15, 16]. OCA is indicated for the treatment of PBC in combination with UDCA in adults with an inadequate response to UDCA, or as monotherapy in adults unable to tolerate UDCA. OCA is not yet in wide clinical use. It has a similar mechanism of action as UDCA but has been shown to achieve further reductions in ALP levels in patients with inadequate response to UDCA. This additional anti-cholestatic effect was associated with a reduction in hepatocellular damage, as shown by decreases in AST and ALT levels. However, OCA treatment achieved only small reductions in these markers of hepatocellular injury which failed to normalize to below the upper limit of the normal reference range [17]. Over time, this sustained hepatocellular injury likely contributes to progressive liver fibrosis and failure. Separately, OCA worsens the severity of pruritus, a key symptom of PBC which significantly impacts patients' quality of life. The currently available therapies mainly target cholestasis. However, there is a need for well-tolerated therapies able to address additional components of the disease, including autoimmune injury to biliary endothelial cells, bile acid-mediated hepatocellular injury, and fibrogenesis [18, 19].

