## Pruritus VAS

Pruritus will be self-assessed by the subject using a Pruritus VAS (see Appendix D) at baseline/Day 1 (Visit 2), Week 12 (Visit 5) and Week 24 (Visit 7). To capture the intensity of itching within the 24 hours preceding these visits, subjects are to be asked to write a number from 0 to 10 below the horizontal scale, with no decimal. Subjects should not mark a cross on the actual horizontal line, nor should the line be measured to obtain a value.

VAS Score (Scale is 0 to 10)	Meaning
0	No pruritus
>0 but <4	Mild pruritus
>4 but <7	Moderate pruritus
>7 but <9	Severe pruritus
>9	Very severe pruritus

Table 6	Pruritus VAS	Assessment	[66]
		Assessment	

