## APPENDIX D: PRURITUS VAS

Guidance on completing the pruritus VAS:

- Write the number between 0 and 10 underneath the scale which best represents the intensity of your itch over the last 24 hours. Do not include a decimal.
- A score of 0 = no itch; a score of 10 = maximum itch, i.e., severe, continuous, day and night intolerable itch.
- Do not mark a cross on the actual line.

Score in the last 24 hours: \_\_\_\_\_\_ (write the number from 0 to 10 which best represents the intensity of your itch, with no decimal).

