## APPENDIX E: PBC-40 QUESTIONNAIRE

Protocol No.: GSN000300 Protocol Version No.: Final 4.0; Amendment 3 Protocol Date: 24 July 2018 Compound No.: GKT137831 Sponsor: Genkyotex Author: Cmed Clinical Services

P	a	ti	e	n	t	Ι	D

For each statement, please circle the response that comes closest to how you feel. If any of the statements do not apply to you please circle 'does not apply'.

Can you say how often the following statements about digestion and diet applied to you IN THE LAST FOUR WEEKS?

1	I was able to eat what I liked	Never	Rarely	Sometimes	Most of the time	Always	
2	I ate or drank only a small amount, and still felt bloated	Never	Rarely	Sometimes	Most of the time	Always	Did not
3	I felt unwell when I drank alcohol	Never	Rarely	Sometimes	Most of the time	Always	apply /never drink alcohol

And IN THE LAST FOUR WEEKS, how often did you experience any of the following?

4	I had discomfort in my right side	Never	Rarely	Sometimes	Most of the time	Always
5	I had dry eyes	Never	Rarely	Sometimes	Most of the time	Always
6	My mouth was very dry	Never	Rarely	Sometimes	Most of the time	Always
7	I had aches in the long bones of my arms and legs	Never	Rarely	Sometimes	Most of the time	Always

Some people with PBC experience itching. How often did you experience itching IN THE LAST FOUR WEEKS? If you did not itch, please circle 'does not apply'

8	Itching disturbed my sleep	Never	Rarely	Sometimes	Most of the time	Always	Did not apply/ no itch
9	I scratched so much I made my skin raw	Never	Rarely	Sometimes	Most of the time	Always	Did not apply/no itch
10	I felt embarrassed because of the itching	Never	Rarely	Sometimes	Most of the time	Always	Did not apply/no itch

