• Absolute and percent change in serum levels of collagen fragments (ProC3, ProC5, C3M, C4M, and BGM) from baseline to Weeks 12 and 24 visits.

Absolute serum levels of collagen fragments and absolute changes from baseline to Week 12 and Week 24 visits in serum levels of collagen fragments will be provided at baseline, Week 12 and Week 24 visits for each allocated treatment group using summary statistics.

The percent change from baseline to Week 12 visit in serum level of collagen fragments will be analyzed using an ANCOVA with the allocated treatment and disease severity at baseline as fixed effects, and the baseline serum level of collagen fragments as a continuous covariate.

The percent change from baseline to Week 24 visit in serum level of collagen fragments will be analyzed similarly.

• Absolute change in Quality of Life scores (based on the 6 domains of the PBC-40 Questionnaire) and Pruritus score (based on Pruritus VAS) from baseline to Weeks 12 and 24 visits.

The PBC-40 questionnaire will be summarized by domain using the scoring described in the coded-PBC-40 document.

If data are missing from a domain (typically missed or duplicated answers), the whole domain should be discarded if <50% of the items are completed. If >50% of the items have responses then the median value for the completed items in the domain should be ascribed to the missing items.

For each of the 6 domains (symptoms, itch, fatigue, cognition, social, emotional), the total scores as well as the absolute and percent changes from baseline to Week 12 and Week 24 visits in the domain's total scores will be provided at baseline, Week 12 and Week 24 visits for each allocated treatment group using summary statistics.

The Pruritus scores will be summarized similarly.

Tertiary efficacy endpoints

The summaries and analyses planned for the tertiary efficacy endpoints are described below.

• Absolute and percent change in serum level of total bile acids from baseline to Weeks 12 and 24 visits.

Absolute serum level of total bile acids and absolute changes from baseline to Weeks 12 and 24 visits in serum level of total bile acids will be provided at baseline, Week 12 and Week 24 visits for each allocated treatment group using summary statistics.

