8.7.4 Subgroup Analysis

Subgroup summaries/analyses will be performed using the following subgroups of interest:

- Subgroups of interest 1: subjects with GGT values below and above the stratification cut off value (≥2.5xULN) (for the primary efficacy endpoint analysis only)
- Subgroups of interest 2: subjects with hsCRP value below and above the ULN at Baseline (for the analysis of hsCRP only).

- Subgroups of interest 3: subjects with ELF score value below 9.8 at Baseline and subjects with ELF score value equal to or greater then 9.8 at Baseline (for the analysis of ELF scores only).
- Subgroups of interest 4: subjects with liver stiffness value below 9.6 kPa at Baseline and subjects with liver stiffness value equal to or greater than 9.6 kPa at Baseline (for the analysis of liver stiffness only).
- Subgroups of interest 5: subjects with any Baseline pruritus VAS value and subjects with a Baseline pruritus VAS value greater than 0.

For each subgroup of interest, any subject with a missing/unknown result will be excluded from the subgroup summaries/analyses.

Subgroup summaries/analyses will only be performed for a minimum subgroup size of at least 20% of the analyzed population, unless otherwise specified.

For a given endpoint, the subgroup summaries/analyses will be run on each of the analysis populations considered for the global summaries/analyses unless otherwise specified.

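### Pruritus VAS and PBC-40 are the only secondary endpoints without a modelled difference from placebo, and VAS percent change drops every subject who starts without itch

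*SAP*

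**What the plan says.** SAP 8.7.2, secondary efficacy endpoints, deals with patient-reported outcomes last. For each PBC-40 domain it will provide "the total scores as well as the absolute and percent changes from baseline to Week 12 and Week 24 visits", and the form of the output is "for each allocated treatment group using summary statistics". For the VAS it adds only: "The Pruritus scores will be summarized similarly". No model, between-arm difference, confidence interval or p-value is named for either instrument. The bullet introducing these endpoints lists absolute change only, while the text beneath it adds percent change. Protocol sections 3 and 10.4.2.2 list both.

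In Protocol 8.1.6 subjects are asked to "write a number from 0 to 10 below the horizontal scale, with no decimal", and Appendix D fixes the ends of the scale: "A score of 0 = no itch; a score of 10 = maximum itch". The inclusion criteria (Protocol 5.2) do not require itch.

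SAP 8.7.4 sets up a pruritus subgroup pair: everyone with a baseline value, and "subjects with a Baseline pruritus VAS value greater than 0". There is no group for baseline 0. Neither SAP 6.2 (missing data) nor SAP 6.5 (baseline) has a rule for percent change when the baseline is zero.

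**The concern.** There are two linked gaps.

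The first is that no difference from placebo is estimated for itch, fatigue or quality of life. Itch matters here because the protocol's own background (section 2.1.1) says of the existing second-line drug that "OCA worsens the severity of pruritus", and argues for well-tolerated alternatives. A reader of the study report will want to know how each dose compares with placebo on itch and how precisely. The plan leaves that to be judged by eye from columns of means and SDs.

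The second is that one of the two planned change measures for the VAS excludes exactly the subjects in whom itch could newly arise. The subgroup with baseline above 0 shows that zeros are expected, but it does not help, because it leaves out the same subjects.

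**Working it through.** **The plan's own figure.** The plan states no precision or power for these endpoints. The only figure used below is 34 per arm (102 in total), from the primary-endpoint sample size in SAP 5.4. That figure reproduces: with SDs of 30 and 40, a difference of 28 and two-sided alpha 0.023475, simulated Wilcoxon power at 34 per arm is 80.2%, against the stated 80%. It does not otherwise bear on this point.

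**Which secondary endpoints in SAP 8.7.2 have a model with a treatment term**

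| Endpoint | Planned analysis |
|---|---|
| GGT, ALP, hsCRP, ALT, AST, total bilirubin | Repeated-measures ANCOVA, all post-baseline visits |
| ELF, collagen fragments | ANCOVA at Week 12 and at Week 24 |
| Fibrinogen, conjugated bilirubin, FIB-4, APRI, liver stiffness | ANCOVA at Week 24 |
| PBC-40 domains, pruritus VAS | Summary statistics only |

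**Percent change at baseline 0.** Percent change = 100 × (post − baseline) / baseline, which has no value at baseline 0. The share of subjects at 0 is not in the documents. Protocol 2.1.1 says up to 60% of patients are asymptomatic at diagnosis, but that concerns diagnosis and all symptoms, so it is only a loose guide. Over an assumed range:

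- 20% itch-free: 34 × 0.8 = 27.2, about 27 per arm contribute.
- 40% itch-free: 34 × 0.6 = 20.4, about 20 per arm.
- 60% itch-free: 34 × 0.4 = 13.6, about 14 per arm.

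**What the two measures show.** Take an invented arm of 34 in which 10 start at 0, 5 of those rise to 4, and the other 29 do not change.

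- Mean percent change: 0%, on n = 34 − 10 = 24.
- Mean absolute change: (5 × 4) / 34 = +0.59 points, on n = 34.
- New itch: 5 of 10 subjects who started at 0.

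Percent change shows nothing, absolute change shows a diluted signal, and the count shows it directly.

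Among subjects above 0 the percent scale is also lopsided. Going from 1 to 2 is +100% and from 10 to 9 is −10%; the largest possible fall is 100%, the largest possible rise (1 to 10) is 900%.

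**What a comparison would deliver.** The documents give no SD for VAS change, so this is illustration. The 95% CI half-width is t × SD × √(2/34), with t on 102 − 5 = 97 degrees of freedom.

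- Assumed SD 2: ±0.96 points unadjusted; × √(1 − 0.5²) = ±0.83 with baseline adjustment at an assumed correlation of 0.5.
- Assumed SD 3: ±1.44 unadjusted; ±1.25 adjusted.

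**The case against.** The strongest reply is that descriptive reporting is what the protocol promised. Protocol 10.4.3.3 commits models to GGT, ELF and ALP, allows them for other liver tests, and otherwise offers summary statistics. Both documents say that the study is not powered for secondary endpoints. This stands: the SAP has not dropped a promised test. It does not settle the matter, because the SAP went beyond the protocol for hsCRP, fibrinogen, liver stiffness, collagen fragments, FIB-4 and APRI and left out only the patient-reported outcomes, without giving a reason. SAP 8.7.2 itself says that inference on secondary endpoints is there to aid interpretation, so lack of power is not the dividing line.

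A reader might infer that there is no placebo comparison at all. That goes too far. Placebo is a displayed arm, and an approximate difference could be worked out from the n, mean and SD shown. What is missing is a planned, baseline-adjusted estimate with its interval.

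A reader might also infer that new itch would go unseen. The documents do not support that. Absolute change is planned for itch-free subjects too, and Protocol 9.2.1 counts anything that emerges or worsens from baseline as an adverse event, with treatment-emergent events tabulated by arm. That backstop is only partial: events are elicited by open questions, and the same section leaves changes in line with natural disease progression to judgement.

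**Conclusion.** The point holds as an analysis gap in unpowered secondary endpoints. It should be corrected, but it does not touch the primary analysis. The missing model and the undefined percent change follow directly from the text. The number of subjects lost from VAS percent change, about 7 to 20 of 34 per arm (34 − 27 and 34 − 14), rests on the assumed 20% to 60% itch-free at baseline.

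The zero-baseline problem is shown for the VAS only. A reader might extend it to all PBC-40 domains. For the itch items the questionnaire says "If you did not itch, please circle 'does not apply", but how that answer is scored is in a separate coding document that is not supplied, and nothing shows that the other five domains can total zero. A reader may also notice that the severity bands in Protocol Table 6, as printed, do not place scores of 4, 7 and 9. No planned analysis uses those bands, so this changes no result.

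**What to change.** 1. In SAP 8.7.2, analyse absolute change in the VAS and in each PBC-40 domain at Weeks 12 and 24 in the ITT population, using the ANCOVA already written for other secondary endpoints (treatment, disease-severity stratum, baseline score). Report each dose minus placebo with a 95% CI. Where residuals are clearly non-normal, use the stratified rank test that SAP 8.7.1 holds in reserve for the primary endpoint. Keep the missing-data rules already set for these endpoints.
2. Tabulate by arm the subjects who go from VAS 0 to above 0, out of those starting at 0, and those above 0 at baseline whose score rises.
3. Either restrict VAS percent change to subjects with baseline above 0 and print that n, or drop it. Because percent change is a protocol-listed endpoint, dropping it must be recorded in SAP section 10 as a departure.
4. Make the bullet and its text agree on whether percent change is reported.
5. Check the PBC-40 coding document. If a domain total can be zero, apply item 3 to that domain; otherwise its percent change can stay.

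The cost is a few extra tables from a model already specified, with no new data. Seven scores × two doses × two visits gives 28 estimates, so they must be labelled supportive, with no claim of confirmed effect.

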## **3** OBJECTIVES AND ENDPOINTS

OBJECTIVE	ENDPOINT (OUTCOME MEASURE)
To evaluate the efficacy of oral GKT137831 in comparison with placebo, in subjects with PBC receiving UDCA and with persistently elevated serum ALP.	Primary efficacy endpoint:
	
 
The percent change from baseline to Week 24 (Visit 7) in serum GGT.
 

	Secondary efficacy endpoints:
	• Absolute and percent change in serum GGT from baseline to each assessment.
	• Absolute change in ELF score from baseline to Weeks 12 and 24.
	• Absolute and percent change in serum ALP from baseline to each assessment.
	• Absolute and percent change in serum levels of hsCRP, and fibrinogen, from baseline to each assessment.
	• Absolute and percent change in serum ALT, AST, conjugated and total bilirubin, from baseline to each assessment.
	• Absolute and percent change in the FIB-4 and APRI scores, from baseline to each assessment (FIB-4: age (years) x AST (IU/L)/(platelet count (10  /L) x (ALT (IU/L)  , APRI: AST (IU/L)/ upper normal limit AST)x100/platelet count (10  /L).
	• Absolute and percent change in liver stiffness as assessed by transient elastography (FibroScan ® or similar technology), from baseline to Week 24, in subjects with values at baseline and Week 24.
	• Absolute and percent change in serum levels of collagen fragments indicative of collagen formation and degradation, from baseline to Weeks 12 and 24.
	Absolute and percent change in Quality of Life (QoL), Fatigue and Pruritus scores based on the PBC-40 and Pruritus Visual Analogue Score (VAS), from baseline to Weeks 12 and 24.

.

	Tertiary efficacy endpoints:
	• Absolute and percent change in total bile acid levels from baseline to Week 12 and 24.
	• Proportion of subjects achieving a 15, 20, 30 and 40% reduction in serum ALP from baseline to each assessment.
	• Proportion of subjects who meet the definition of PBC responder criteria applying the Paris I, Toronto I, Toronto II, Toronto III, Toronto IV, Mayo II, and Barcelona disease prognostic risk criteria at Weeks 12 and 24.
	Exploratory Endpoints:
	• Optionally, absolute and percent change in serum C4 and FGF19 from baseline to Weeks 12 and 24.
	• Optionally, absolute and percent change in serum interleukin (IL)-6 and cytokeratin-18 (CK-18), from baseline to Weeks 12 and 24.
	
 
Optionally, absolute and percent change in serum IgM, IL-4, IL- 12, IL-17A, and interferon γ, from baseline to Weeks 12 and 24.
 

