### **10.4.2.3** Tertiary Efficacy Endpoints

- Absolute and percent change in total bile acid levels from baseline to Weeks 12 and 24.
- Proportion of subjects achieving a 15, 20, 30 and 40% reduction in serum ALP from baseline to each assessment.
- Proportion of subjects who meet the definition of PBC responder criteria applying the Paris I, Toronto I, Toronto II, Toronto III, Toronto IV, Mayo II and Barcelona disease prognostic risk criteria at Weeks 12 and 24.

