With regard to the PBC-40, analysis is by domain, with the scoring explained in the coded-PBC-40. Data should be considered by domain rather than in terms of a cumulative PBC-40 score. If data are missing from a domain (typically missed or duplicated answers) the whole domain should be discarded if <50% of items are completed. If >50% of responses are present then the median value for the completed items in the domain should be ascribed to the missing item.

The number and percentage of subjects belonging to each group for categorical efficacy endpoints will be presented by visit and treatment group. Such endpoints include but are not limited to, responders to the Paris I, Toronto I, Toronto II, Toronto III, Toronto IV, Mayo II, and Barcelona disease prognostic risk criteria for PBC.

All descriptive statistics will be presented overall, by treatment severity and by any other appropriate subgroups as defined in the SAP provided sufficient subject numbers are available within each subgroup level, within each treatment group.

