The percent change from baseline to Week 12 visit in serum level of total bile acids will be analyzed using an ANCOVA with the allocated treatment and disease severity at baseline as fixed effects, and the baseline serum level of total bile acids as a covariate.

The percent change from baseline to Week 24 visit in serum level of total bile acids will be analyzed similarly.

- **Proportion of subjects who meet the definition of PBC responder** applying the following two criteria:
 - ALP < 1.67xULN
 - ALP < $1.67 \times ULN$, ALP reduction $\ge 15\%$, and total bilirubin < ULN (composite criterion)

For each of the two above PBC response criteria, the proportion of responders at Weeks 12 and 24 visits will be presented for each allocated treatment group.

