The interim analysis will be conducted by the unblinded SMB statistician, who has no involvement with the study conduct. The interim analysis outputs will be communicated to the Sponsor's Chief Medical Officer.

The interim analysis described above does not include assessments of safety data. The safety data will be reviewed periodically and separately as described in the study SMB charter.

10 Changes to Planned Analyses

The final analysis will be performed according to a 2-stage process detailed in Section 6.1.

11 Document History

Date	Version	Modified by	Brief details of changes made to template
150CT2018	1.0	[name]	Initial final version
15MAR2019	2.0	[name]	Updated final version The main changes are the following: 1. Addition of Section 6.1 to clarify the timing of the final analysis. 2. Addition of Appendix 1 to provide the list of Top Line tables.

12 References

[1] New Drug Application (NDA) 207999 submitted by Intercept Pharmaceuticals, Inc. for obeticholic acid (OCA) proposed for the treatment of Primary Biliary Cirrhosis (PBC), Gastrointestinal Drug Advisory Committee (GIDAC) Meeting, April 7th, 2016.

[2] Hirschfield GM et al. Efficacy of Obeticholic Acid in Patients With Primary Biliary Cirrhosis and Inadequate Response to Ursodeoxycholic Acid. Gastroenterology 2015; 148: 751-761.

[3] CTCAE v4.03:

http://evs.nci.nih.gov/ftp1/CTCAE/CTCAE_4.03_2010-06-14_QuickReference_5x7.pdf

13 Appendix 1: List of Top Line tables

Table order	Table number	Table title
1	14.1-1	Subject Disposition (Randomized Population)
2	14.1-3	Summary of Demographic and Baseline Characteristics (ITT Population)
3	14.1-5.1	Disease Characteristics (ITT Population)
4	14.2-1.1.1	Summary of Absolute and Percent Change from Baseline to Week 24 Visit in Serum GGT (ITT Population)
5	14.2-1.1.2	Analysis of Percent Change from Baseline to Week 24 Visit in Serum GGT (ITT Population)
6	14.2-1.3.1.1	Summary of Percent Change from Baseline to Week 24 Visit in Serum GGT by Subgroup of Baseline GGT values (ITT Population)
7	14.2-1.3.1.2	Analysis of Percent Change from Baseline to Week 24 Visit in Serum GGT by Subgroup of Baseline GGT values (ITT Population)
8	14.2-2.1.1	Summary of Absolute and Percent Change from Baseline to each Post- Baseline Visit in Serum GGT (ITT Population)
9	14.2-2.1.2	Analysis of Percent Changes from Baseline in Serum GGT across all Post Baseline Visits [a] Model Estimates (ITT Population)

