28	14.2-15.2	Summary of Change from Baseline to Week 24 Visit in each Domain Score of the PBC-40 Questionnaire (ITT Population)
29	14.2-16	Summary of Change from Baseline to Week 12 and Week 24 Visits in Pruritus Score (VAS) (ITT Population)
30	14.2-17	PBC Responders Rates at Week 12 and 24 Visits Applying Two Response Criteria: Serum ALP < $1.67xULN$ and Combined Criterion Serum ALP < $1.67xULN$, ALP Reduction \geq 15%, and total bilirubin < ULN (ITT Population)

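### The SAP reports the PBC responder endpoint by two ALP-based criteria instead of the seven criteria the protocol names, and does not declare the change

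*SAP*

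**What the plan says.** The protocol names the responder criteria in three places. Its objectives and endpoints table (Section 3) lists, under tertiary efficacy endpoints, the "Paris I, Toronto I, Toronto II, Toronto III, Toronto IV, Mayo II, and Barcelona disease prognostic risk criteria at Weeks 12 and 24". Section 10.4.2.3 repeats the endpoint as the proportion of responders "applying the Paris I, Toronto I, Toronto II, Toronto III, Toronto IV, Mayo II and Barcelona disease prognostic risk criteria" at the same two visits. Section 10.4.3.3 says that counts and percentages for categorical endpoints will be shown by visit and treatment group, and gives as examples "responders to the Paris I, Toronto I, Toronto II, Toronto III, Toronto IV, Mayo II, and Barcelona disease prognostic risk criteria for PBC".

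SAP Section 8.7.2 has a tertiary endpoint with the same responder label, evaluated "applying the following two criteria". The first is "ALP < 1.67xULN". The second is a composite of that cut, an ALP reduction of at least 15% and total bilirubin below ULN. The SAP will present proportions for these two at Weeks 12 and 24. The matching output is Table 14.2-17 in SAP Appendix 1, titled "PBC Responders Rates at Week 12 and 24 Visits Applying Two Response Criteria".

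SAP Section 10, which is the place for changes to planned analyses, has one entry: "The final analysis will be performed according to a 2-stage process detailed in" Section 6.1. The SAP's document history gives as the main changes in version 2.0 the addition of Section 6.1 and of Appendix 1.

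**The concern.** A programmer who follows the SAP will not produce the responder endpoint as the protocol names it. A reader of the report who checks SAP Section 10 for departures will conclude that the endpoint is unchanged.

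Responder endpoints are sensitive to their definition: the same laboratory data can give different rates under different cuts. When the definition changes between protocol and SAP, the reader needs to know that it changed, why, and when in relation to any unblinded look at the data. This trial has an unblinded Week 6 interim analysis that includes ALP and total bilirubin, the components of the two SAP criteria. That makes the date of the change worth recording. At stake is the traceability of one tertiary endpoint and protection against a charge of selective reporting.

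**Working it through.** The plan gives no rate, power or alpha for this endpoint, so there is no figure to reproduce. The check compares the texts.

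**Step 1. Same endpoint or a different one?** The label, the tertiary rank and the visits (Weeks 12 and 24) agree between Protocol 10.4.2.3 and SAP 8.7.2. Only the criteria differ. This is one endpoint redefined, not two separate endpoints.

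**Step 2. Criteria side by side.**

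| | Protocol 3, 10.4.2.3, 10.4.3.3 | SAP 8.7.2, Table 14.2-17 |
|---|---|---|
| Criteria | Paris I, Toronto I, II, III, IV, Mayo II, Barcelona | ALP < 1.67 x ULN; ALP < 1.67 x ULN with ALP reduction >= 15% and total bilirubin < ULN |
| Number | 7 | 2 |
| Shared by name | 0 | 0 |

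None of the seven names occurs in the supplied SAP text. Neither the 1.67 x ULN cut nor the composite occurs in the supplied protocol text.

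**Step 3. Size in reported rates.** Assume one rate per criterion per visit; the protocol does not spell this out. The protocol then implies 7 x 2 = 14 responder rates per arm, and the SAP plans 2 x 2 = 4.

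**Step 4. Could this be a version lag?** No. SAP Section 3 says that it refers to Protocol Version 4.0 (Amendment 3, 24 July 2018). That is the version supplied, and it still carries the seven criteria.

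**Step 5. Did the protocol leave the choice to the SAP?** It explicitly defers the contents of the interim analysis (10.3), per-protocol sensitivity analyses of secondary endpoints (10.4.3.3) and missing-data details (10.4.3.7). It does not defer the responder definitions.

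**Step 6. Was the change declared?** SAP Section 10 lists only the 2-stage final analysis. The document history does not mention responder criteria either, though it claims to list only the main changes.

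**Step 7. Can the timing be established?** SAP version 1.0 is dated 15 October 2018 and version 2.0 is dated 15 March 2019. Neither document dates the interim analysis, and version 1.0 is not among the documents. Whether the criteria were set before or after the interim cannot be determined.

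**The case against.** Several points on the other side stand.

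- **Overlap.** Neither document gives a threshold or component for any of the seven named criteria. A SAP criterion may coincide numerically with one of them. The finding is therefore about what is named and declared. It does not show that all seven are lost in substance.
- **Something is reported.** A reader might infer that the responder endpoint disappears. It does not: responder proportions are still given at both visits, and SAP 8.7.2 also keeps the proportions with 15, 20, 30 and 40% ALP reduction.
- **Prominence.** A reader might infer that the substitute is being headlined. It is in the top-line package, but as the last of 30 tables, and its title spells out both definitions.
- **Additions are allowed.** Protocol 10.4.3.3 describes its list of categorical endpoints as non-exhaustive, so adding two ALP-based criteria is no departure. That wording does not cover leaving out the ones listed.
- **Data-driven choice.** A reader might infer that the definitions were picked after the interim results. The documents do not support this. The interim is undated, covers Week 6 only and excludes responder rates. It is run by a statistician with no part in study conduct, and the version 2.0 history lists no change to the criteria. SAP Section 9 does send the outputs to the sponsor's Chief Medical Officer, but nothing links that to this choice. Section 10 is also silent on another departure: Protocol 10.4.3.7 plans MAR or MNAR imputation, and SAP 6.2 uses LOCF. That points to an incomplete change record.
- **Rank.** The endpoint is tertiary, with no test attached, and SAP 8.7.2 already advises caution in reading such endpoints.

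These limit the size of the point. They do not explain why named criteria were left out without a declaration.

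**Conclusion.** The point holds as one of consistency and declaration. The protocol names seven responder criteria. The SAP, citing that same protocol version, reports two criteria that are not in the protocol text, and Section 10 does not say so. By name, 0 of 7 criteria are carried over and 0 changes to this endpoint are declared. If the SAP is followed, the endpoint is not reported as the protocol names it.

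This rests on the supplied text of both documents and on reading the protocol's list as a commitment to report each named criterion. It does not assume that the seven differ numerically from the two, or that anyone chose definitions after seeing results. The primary GGT analysis, its alpha and its power are untouched. The point should be corrected, but it does not threaten the trial's main conclusion.

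**What to change.** In SAP Section 8.7.2, restore the seven named criteria at Weeks 12 and 24 as the tertiary responder endpoint, and write out the definition of each. Keep the two ALP-based criteria, labelled as additional, and extend the responder output to match.

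In SAP Section 10, list the addition of the two criteria with the reason and the date relative to the interim analysis. If any named criterion is deliberately dropped, for instance because it duplicates another once the definitions are written down, declare and justify that there before unblinding.

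The cost is SAP wording and one descriptive table. This assumes that the seven criteria can be computed from laboratory values already collected. Protocol 8.2.1 provides ALP, AST, ALT, conjugated and total bilirubin and albumin at each visit, but the assumption can be confirmed only once the definitions are written.
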